For individuals who express suicidal ideation at any time during the study, staff will administer the Columbia Suicide Severity Rating Scale, which distinguishes passive from active suicidal ideation, and includes specific questions on level of intention and controllability, and any specific plans of self-harm. Staff members are instructed that participants who state that they have considered suicide, have a plan, and either intend to harm themselves, or may not be able to prevent themselves from self-harm, represent an immediate risk. If it is detected during the in-home assessments or intervention visits, staff will be advised to contact [name] ASAP, who will then talk with the participant to assess the risk, and determine an appropriate course of action. If the participant does not pose an immediate risk, staff will nevertheless notify [name], who will contact the participant within 24 hours to assess the participant and devise a plan of treatment, or recommend a course of action to study staff.

b. Cognitive Impairment: If incident cognitive impairment and/or functional disability (e.g. difficulty managing medications) is detected, staff will contact [name] to identify diagnostic/treatment steps to ensure adequate evaluation, treatment, and safety.

c. Abuse or Neglect: If staff determines that a participant is a victim of abuse or neglect, after discussion with [name], we will file a report with the appropriate agency that services the area in which the participant lives.

All research procedures are designed to ensure participants' confidentiality. We will assign each participant a unique identification number; this ID number will be the only identifying information on data forms. Participants' names will not appear on interview forms. A list linking ID numbers to names will be kept in a password-protected computer file accessible only to project staff. Audiotapes of interview and/or intervention sessions to monitor treatment fidelity will be identified by the unique identifier and will not contain participants' names or any identifying information.

Because this study is testing a low risk behavioral/educational intervention, there are no circumstances in which participants will be involuntary discontinued from the study.

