10.6.3. DSMB Responsibilities

The DSMB responsibilities will include:

- Reviewing the research protocol, informed consent documents and plans for data safety and monitoring;
- Recommending that participant recruitment be initiated after receipt of a satisfactory protocol:
- Evaluating the progress of the trial, including periodic assessments of data quality and timeliness, recruitment, accrual and retention, participant risk versus benefit, and other factors that can affect study outcome;

- Considering factors external to the study when relevant information becomes available, such as scientific or therapeutic developments that may have an impact on the safety of the participants or the ethics of the trial;
- Reviewing study performance, making recommendations and assisting in the resolution of problems reported by the PI;
- Protecting the safety of the study participants;
- Making recommendations to the PI concerning continuation, termination or other modifications of the trial based on the observed beneficial or adverse effects of the treatment under study; and
- Ensuring the confidentiality of the study data and the results of monitoring.

11: PSYCHIATRIC EMERGENCY PLAN

To detect suicidal ideation, the Outcome Assessor administers the Patient Health Questionnaire-9, which includes a question asking if the participant has thoughts that he/she would be better off dead or has had thoughts of hurting him/herself. If a participant endorses suicidal ideation, intent, or plan, staff is trained to follow a protocol. The protocol entails a specific determination of the suicidal risk and prescribes a set of actions.

For individuals who express suicidal ideation at any time during the study, staff will administer the Columbia Suicide Severity Rating Scale. Staff members are instructed that participants who have suicidal thoughts, or who express imminent intent with or without a method of self-harm, represent an immediate threat. Staff will contact [name], who will talk with the participant to assess the level of risk and determine an appropriate course of action. If the participant does not pose an immediate threat, staff will nevertheless notify [name], who will contact the participant within 24 hours to assess the participant and devise a plan of treatment.

All staff will be trained to implement the study Psychiatric Emergency Plan when indicated. The plan is as follows:

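### Sections 10.3.1(a) and 11 define immediate suicide risk differently; prompt-call instructions elsewhere keep the practical gap small, but Section 10.3.1(a) should defer to Section 11.

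*Combined protocol and SAP*

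**What the plan says.** Section 10.3.1(a) has staff give the Columbia Suicide Severity Rating Scale to anyone who expresses suicidal ideation. It describes the scale as one "which distinguishes passive from active suicidal ideation, and includes specific questions on level of intention and controllability, and any specific plans of self-harm". It then states that participants who report having thought about suicide, and who also "have a plan, and either intend to harm themselves, or may not be able to prevent themselves from self-harm, represent an immediate risk". The next sentence reads "If it is detected during the in-home assessments or intervention visits, staff will be advised to contact [name] ASAP", after which the clinician talks with the participant. The other branch begins "If the participant does not pose an immediate risk, staff will nevertheless notify" and allows clinician contact within 24 hours.

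Section 11 starts from the same point, expressed ideation followed by the Columbia scale. Its rule is that "participants who have suicidal thoughts, or who express imminent intent with or without a method of self-harm, represent an immediate threat". For these participants, "Staff will contact [name], who will talk with the participant to assess the level of risk"; no time is given. Its other branch is "If the participant does not pose an immediate threat, staff will nevertheless notify" the clinician, "who will contact the participant within 24 hours to assess the participant and devise a plan of treatment".

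Neither section refers to the other's definition.

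**The concern.** One manual gives the same staff two rules for the same decision. Section 10.3.1(a) makes a plan part of the definition. Section 11 does not, and says that a method is not needed. The case that matters most is a participant who intends self-harm, or may be unable to prevent it, but has no plan. Section 11 calls that participant an immediate threat. Section 10.3.1(a), read literally, leaves that participant on the 24-hour branch.

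At stake is how soon the clinician speaks with such a participant. This is a participant-safety procedure; no analysis depends on it.

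**Working it through.** The plan gives no figure to reproduce. The check sets the two rules side by side and then asks which other instructions bear on timing.

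**Step 1: the rules as logic.** Take a participant who already has suicidal thoughts, and vary three features that the Columbia scale covers: plan, intent, and possible inability to prevent self-harm. That gives 2 × 2 × 2 = 8 profiles.

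- Section 10.3.1(a): immediate if plan AND (intent OR inability).
- Section 11 as written: immediate if suicidal thoughts OR imminent intent.
- Section 11 read narrowly: immediate if intent, with or without a method.

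The grid treats intent and imminent intent as the same thing.

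| Plan | Intent | Inability | 10.3.1(a) | 11 as written | 11 narrow |
|---|---|---|---|---|---|
| yes | yes | yes | immediate | immediate | immediate |
| yes | yes | no | immediate | immediate | immediate |
| yes | no | yes | immediate | immediate | not |
| yes | no | no | not | immediate | not |
| no | yes | yes | not | immediate | immediate |
| no | yes | no | not | immediate | immediate |
| no | no | yes | not | immediate | not |
| no | no | no | not | immediate | not |

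Section 10.3.1(a) classes 3 of 8 as immediate and Section 11 as written classes 8 of 8, so they disagree on 8 − 3 = 5. On the narrow reading Section 11 classes 4 of 8, and they disagree on 3: intent without a plan (2 profiles), and plan plus inability without intent (1 profile). Intent without a plan is in conflict on either reading.

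These are counts of logical cells with no weights. They show that the rules differ and where. They do not say how many participants are affected, and the documents give no such count.

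**Step 2: what governs the call from staff to clinician.**

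- Section 7.9 says the procedures are built around a low threshold for alerting the clinician.
- Section 10.3.1, before item (a), has staff call the PI for psychiatric emergencies and gives suicidal ideation as the example.
- The steps in Section 11 start when a participant voices thoughts of death or suicide. If the participant indicates, or staff suspect, a wish not to go on living, staff give the Columbia scale, call as soon as possible, and remain in the home until they have spoken with the clinician.
- Appendices 3 and 4 direct an immediate call for suicidal ideation and name a backup contact.

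None of these depends on a plan.

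**Step 3: what governs the conversation between clinician and participant.** The steps in Section 11 say only that the clinician will probably ask to speak with the participant. The definitions in Sections 10.3.1(a) and 11 are the only texts that tie this conversation to a risk level with a time limit, and they conflict. The difference is therefore at most 24 hours in that conversation.

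**The case against.** The strongest reply is that Section 11 is the working procedure. All staff are trained on it, and Appendices 3 and 4 send staff to it in a severe crisis. Following it, staff reach the clinician with the Columbia answers in hand while still in the home. A later conversation would then be the clinician's decision, not a sorting error by staff. This largely stands, and it is why the gap is small. It does not remove the conflict: Section 10.3.1(a) does not point to Section 11, and Section 7.1 requires every team member to read the whole manual.

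A second reply is that Section 10.3.1(a) never says that only participants with a plan are at immediate risk, and that the word it in "If it is detected during the in-home assessments or intervention visits, staff will be advised to contact [name] ASAP" may mean any ideation. On that reading every case found at a visit gets a prompt call and a conversation. The ambiguity is real. But the branch beginning "If the participant does not pose an immediate risk, staff will nevertheless notify" needs some rule for who is not immediate, and the plan-based list is the only one that the section offers.

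A reader might also go further than the documents allow:

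- That participants with intent but no plan would go unreported. Both sections have the clinician notified in either branch.
- That the cell counts measure how often the conflict would arise. They do not. Suicidal patients are also excluded at screening (Sections 2 and 5.3), and severe depression is a listed reason for ineligibility (Section 5.5).
- That Section 11's definition leaves its 24-hour branch with no one in it and should be narrowed. Any non-zero answer to the PHQ-9 item, which includes thoughts of being better off dead, leads to the Columbia scale, and Appendix 4 provides for participants found to have no ideation. Narrowing Section 11 would also weaken the safer of the two rules.

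**Conclusion.** The inconsistency is real and should be corrected. For intent without a plan it holds on either reading of Section 11; its application to Section 10.3.1(a) rests on reading that list as the rule that sorts participants between the two branches.

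Its practical size is small. It concerns the time at which the clinician speaks with the participant, with 24 hours as the upper limit and no frequency available. Instructions elsewhere in the manual already favor the broader rule and a prompt call. The documents do not support a finding that participants at risk would be missed, or that the trial's results would be affected.

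**What to change.** 1. In Section 10.3.1(a), delete the plan-based definition and cross-refer to the Psychiatric Emergency Plan in Section 11. For any suicidal ideation found at a visit, with or without a plan or method, staff call the responsible clinician as soon as possible, use the backup contact in Appendices 3 and 4 if needed, and stay until they have spoken.
2. Keep Section 11's definition as broad as it is, and state the same call-and-stay rule beside it, since its immediate branch now gives no time.
3. In both sections, limit the 24-hour route to participants whom the clinician judges during that call not to be at immediate risk. This also settles where a plan without stated intent belongs: staff call, and the clinician decides.
4. Leave participants with no ideation on the Columbia scale on Appendix 4's email route.

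The cost is wording changes in two places, a short staff notice and possibly a few more immediate calls. No new data are needed. Recruitment ended with 156 randomized, and the documents do not say whether home visits continue, so the notice may reach few staff.

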10.3.2. Informed Consent Process

We will follow the informed consent guidelines of Jefferson's Institutional Review Board. The ED staff will obtain informed consent in writing from all participants. They will discuss the objectives, procedures, risks, and benefits of the study. The consent form will describe the baseline assessment and the possibility of not being eligible for further study participation. The consent form will also describe subsequent procedures for eligible persons, including randomization to one of two treatment groups and the follow-up assessment schedule.

10.4. Interim Analysis

PREVENT is not expected to pose any special risks for the participants, and no safety issues are expected that would prompt early termination of the trial. The DSMB will monitor safety, study outcomes and performance data on an ongoing basis. If the DSMB identifies any safety or ethical concerns during the conduct of the trial, it is still possible that they could recommend early termination.

10.5. Data Safety and Monitoring

The Principal Investigator (PI) will be responsible for ensuring participants' safety on a daily basis. The DSMB will monitor participant safety, evaluate the progress of the study, review procedures for maintaining the confidentiality of data, the quality of data collection, management, and analyses.

10.5.1. Frequency of Data and Safety Monitoring

The PI will be informed of serious adverse events as soon as they occur. AEs and Alerts will be reported at regular intervals to be decided upon by the DSMB. The DSMB will meet at least once annually by teleconference call to review study progress, data quality, and participant safety. The DSMB may request teleconference calls if needed.

10.5.2. Content of Data and Safety Monitoring Report

The content of the data and safety monitoring report will include information on: SAEs, AEs, and Alerts; participant accrual (actual accrual vs. expected accrual, reasons for non-eligibility); participant activities (e.g., percent of participants who provided follow-up data at each assessment point, percent of participants who completed initial treatment and booster sessions, percent of participants who withdrew from the study); protocol deviations; descriptive data on baseline characteristics, and any other information requested by the DSMB. Specific requirements for these reports will be defined by the DSMB.

10.6. DSMB Membership and Affiliation

DSMB members will be selected by the PI. Membership will consist of individuals who have no financial, scientific, or other conflict of interest with the trial. Collaborators or associates of the investigator are not eligible to serve on the DSMB. Written documentation attesting to absence of conflict of interest is required. The DSMB will include experts in or representatives of the fields of relevant clinical expertise, clinical trial methodology, and biostatistics.

10.6.1 Conflict of Interest for DSMB

DSMB members should have no direct involvement with the study investigators or intervention. Each DSMB member will sign a Conflict of Interest Statement which includes current affiliations, if any, with pharmaceutical and biotechnology companies (e.g., stockholder, consultant), and any other relationship that could be perceived as a conflict of interest related to the study and/or associated with commercial interests pertinent to study objectives.

10.6.2. Protection of Confidentiality

Data will be presented in a blinded manner during the open sessions of the DSMB or in DSMB reports. At DSMB meetings, data and discussion are confidential. Participant identities will not be known to the DSMB members.

10.6.3. DSMB Responsibilities

The DSMB responsibilities will include:

- Reviewing the research protocol, informed consent documents and plans for data safety and monitoring;
- Recommending that participant recruitment be initiated after receipt of a satisfactory protocol:
- Evaluating the progress of the trial, including periodic assessments of data quality and timeliness, recruitment, accrual and retention, participant risk versus benefit, and other factors that can affect study outcome;

- Considering factors external to the study when relevant information becomes available, such as scientific or therapeutic developments that may have an impact on the safety of the participants or the ethics of the trial;
- Reviewing study performance, making recommendations and assisting in the resolution of problems reported by the PI;
- Protecting the safety of the study participants;
- Making recommendations to the PI concerning continuation, termination or other modifications of the trial based on the observed beneficial or adverse effects of the treatment under study; and
- Ensuring the confidentiality of the study data and the results of monitoring.

11: PSYCHIATRIC EMERGENCY PLAN

To detect suicidal ideation, the Outcome Assessor administers the Patient Health Questionnaire-9, which includes a question asking if the participant has thoughts that he/she would be better off dead or has had thoughts of hurting him/herself. If a participant endorses suicidal ideation, intent, or plan, staff is trained to follow a protocol. The protocol entails a specific determination of the suicidal risk and prescribes a set of actions.

For individuals who express suicidal ideation at any time during the study, staff will administer the Columbia Suicide Severity Rating Scale. Staff members are instructed that participants who have suicidal thoughts, or who express imminent intent with or without a method of self-harm, represent an immediate threat. Staff will contact [name], who will talk with the participant to assess the level of risk and determine an appropriate course of action. If the participant does not pose an immediate threat, staff will nevertheless notify [name], who will contact the participant within 24 hours to assess the participant and devise a plan of treatment.

All staff will be trained to implement the study Psychiatric Emergency Plan when indicated. The plan is as follows:

If at any time severe depression is detected, or if a participant expresses thoughts of death or suicide, staff need to assess their risk for self-harm, and initiate the study Psychiatric Emergency Plan. Signs of severe depression include: poor hygiene or grooming, house in disarray (compared to previous times that the staff has interacted with the participant), weight loss, flat or sad affect, slowed speech, or statements of not wanting to live anymore. If severe depression is suspected, staff will say the following to the subject:

From what you're saying and from what I'm seeing, I suspect you are severely depressed and I'm concerned about this.

If the participant indicates (or you suspect) that they don't want to live anymore, you will need to do a suicide risk assessment by administering the Columbia Suicide Severity Rating Scale. When you are finished administering this scale, please go somewhere private (e.g., another room or your car) and call [name] ASAP. Have the participant's responses to the rating scale with you. Please do not leave the participant's home until you speak with [name]. He will provide guidance on how to handle the situation. He will likely ask to speak with the participant to further assess their risk of self-harm, and he will provide you with instructions for handling the situation immediately after he speaks with the participant.

If [name] determines that the participant is not suicidal, you can say "I'd like to know if you are receiving help for depression. Have you ever talked to a doctor or counselor or social worker about how you are feeling? Are you taking any medication for depression or nerves?" If the participant is currently being treated for depression, encourage them to keep up with the treatment and to let the treating physician know that their depression is not getting better.

If they are not being treated you can say: "It is not uncommon for people with diabetes to become depressed. In fact, it is a known complication of diabetes. But you don't have to feel this way. There

are many different kinds of safe and effective treatments for depression. Some people prefer to be treated with medications and other people decide to talk to a counselor.

Depending on the situation, for participants who have severe depression or a significant worsening of depression, [name] may recommend that you encourage the participant to discuss their depression with their primary care physicians, or that you offer the participant a mental health referral. After you talk to [name], you can convey his recommendation to the participant. You can say something like (based on [name] recommendation):

It seems like you're quite depressed, and it is a good idea to receive treatment. I recommend that you contact your primary care doctor to let them know how you are feeling. Alternatively, I can give you a referral for community-based mental health treatment."

When you get back to the office, please send an email ASAP to the PI, the Project Director, and the Study Coordinator. In the email, please describe the situation in detail and the actions that were taken (e.g., [name] talked to participant and determined that the participant was not in imminent harm, I recommended that the participant contact their PCP). If you recommended to the participant that they contact their PCP or if you made a mental health referral, please contact the participant within 2 to 3 days to determine the outcome of that action (e.g., PCP prescribed medication, participant has upcoming mental health appointment). Please send a follow-up email to the PI, the Project Director, and the Study Coordinator to inform them of the outcome of the referrals/recommendations.

12: DATA MANAGEMENT

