10.3. Protection Against Study Risks

10.3.1. Protection Against Risks

We will minimize the risk of hypoglycemia by having primary care physicians (PCPs) carefully review participants' current medication regimens, previous HbA1c levels, and risk of hypoglycemia based on previous hypoglycemic episodes and other risks. For enrolled participants, PCPs will adjust hypoglycemic medications (e.g., reduce dose of a sulfonylurea) if they are concerned that increased adherence may cause hypoglycemia. We will encourage participants to regularly check their blood glucose, particularly if they feel light-headed, shaky, or weak.

We will minimize the risk of discomfort during assessments and treatment by selecting staff based on their interpersonal sensitivity and capacity to communicate with older persons. We will train staff to recognize signs of distress and fatigue and will terminate testing or treatment if indicated. The assessment instruments have been well-tolerated in our previous studies with African Americans.

We also train the staff to recognize medical events (e.g., hypoglycemia) that warrant intervention at all stages of this project, including screening and follow-up assessments. Since screening will occur in the Emergency Department, medical assistance will be available if needed. For in-home assessments and treatment visits, staff will be instructed to call the PI if they encounter a situation that may warrant medical attention. Events of concern include suicidal ideation, hypoglycemia, HbA1c levels ≥ 10.0% and participant-reported recent blood glucose level over 300, foot ulcers, and any other symptomatic medical condition that the participant reports or that staff observe. For psychiatric emergencies (e.g., suicidal ideation), staff will call PI [name], a geriatric psychiatrist. Conditions of special interest include:

a. Suicidal Ideation: To detect suicidal ideation, staff will administer the Patient Health Questionnaire-9, which includes a question asking if the participant has thoughts that he/she would be better off dead, or has had thoughts of hurting him/herself. If a participant endorses suicidal ideation, staff will be trained to follow a protocol for at-risk participants.

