- 7) This study requires home visits, and thus you may encounter potentially unsafe situations. If you encounter a situation that makes you feel unsafe (e.g., sexually inappropriate comments, gun in plain sight, bad neighborhood), or if you suspect that there is drug use or any other questionable activity going on in the home, you should leave immediately. You can politely say something like "I left some study materials in my car and I'm going to get them". And then just drive away. If you are in the home for an assessment, and the participant asks you for their incentive, you can give them the money, even if the assessment wasn't completed. You do not need to have them sign the receipt in this circumstance. Your safety is the top priority. Another strategy you can employ is to send a text (even a blank text) to [name], [name], or [name]. They will then call you right away to be sure that you are OK. Alternatively, you can ask [name], [name], or [name] to call you at a designated time when you are in a participant's home to check on you. If such an incident occurs, please email or call [name] or

[name] as soon as you can. [name] or [name] will call the participant and notify them that if they wish to continue participating in the study, all visits must occur at Jefferson. The study will cover the cost of the participant's roundtrip travel to Jefferson. Staff will no longer be permitted to make home visits to the participant.

8) If at any time you suspect that a participant is severely depressed, please email [name], [name], and [name] as soon as you can. If you think they are in a severe crisis, please follow the Psychiatric Emergency Plan that is described in the MOP. If the participant has suicidal ideation, please call [name] ASAP. Call [name] if you cannot reach [name].

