 - First, ask to see the participant's medications bottles (or a list of they use a med box), including supplements and over the counter drugs.
 - Second, ask the participant's if they take any other medications that they aren't showing you.
 - Enter the medication names, doses, and number of time per day that they take each medication into REDCap.
- 8) Patient Health Questionnaire (PHQ 9):
 - If the participant seems severely depressed, please email [name], [name], and [name] as soon as you can. If you think they are in a severe crisis, please follow the Psychiatric Emergency Plan.
 - If the participant responds with anything other than "0" for question 9, please administer the Columbia-Suicide Severity Rating Scale.
 - If the participant has suicidal ideation, please call [name] ASAP. Call [name] if you cannot reach [name].
 - If the participant does not have suicidal ideation, please email a description of the participant's responses to the PHQ and the Columbia to [name], [name], and [name].
 - Be sure to include your impressions/observations of the participant.
- 9) After completing an in-home assessment, the Outcome Assessor should not leave the participant's home until they check REDCap to verify that:
 - (1) The correct participant ID was selected.
 - (2) All questionnaires are completed.
 - (3) Missing data are properly coded.

Once the Outcome Assessor gets back to the office, they will enter in REDCap all data that were collected on paper forms (e.g., LAD, MOCA). The Outcome Assessor should also check to be sure that all hard copies are properly labeled with the date of the assessment, the participant's initials and ID, and the assessment type (e.g., 6 months). Assessments should be marked as "unverified". The Outcome Assessor will then email [name], [name], and [name] to inform them that the assessment was completed. The subject line of the email should contain the participant's initials and ID (for example, CRJC0001). The body of the email should contain the following completed table (note example provided). The image of the A1c readout should be attached to the email. The email must be sent within 1 business day of the completion of the assessment.

Notification of Completed Assessment Table

Participant ID:	CRJC00001
Assessment date:	9/14/18
Assessment:	Part 2 Baseline
Comments:	

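### Section 11 starts the Psychiatric Emergency Plan on severe depression alone, but Appendices 3 and 4 ask for an email and keep the Plan for an undefined severe crisis; the gap is mainly at treatment sessions

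*Combined protocol and SAP*

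**What the plan says.** Section 11 joins two triggers with an 'or': "If at any time severe depression is detected, or if a participant expresses thoughts of death or suicide, staff need to assess their risk". The risk meant is self-harm, and the Plan must start. It lists six signs of severe depression, starting with "poor hygiene or grooming, house in disarray". The next explicit step is a script: "If severe depression is suspected, staff will say the following to the subject". The Columbia scale, the private call to the named clinician and the rule against leaving the home come after that and are conditional: "If the participant indicates (or you suspect) that they" no longer want to live. The section closes with the clinician's advice on severe or worsening depression, an email to the PI, Project Director and Study Coordinator once staff are back at the office, and a check within 2 to 3 days on any referral or advice to see the PCP.

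Appendix 3, item 8, addressed to all staff, says: "If at any time you suspect that a participant is severely depressed, please email" certain named staff. It continues: "If you think they are in a severe crisis, please follow the Psychiatric Emergency Plan that is described in the MOP". Appendix 4, item 8, under the PHQ-9 heading for the Outcome Assessor, runs the same way: "If the participant seems severely depressed, please email", with the same severe-crisis condition for the Plan. Both appendices ask for an urgent call when there is suicidal ideation.

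**The concern.** Take a community health worker at a treatment session who sees a participant with marked self-neglect, flat affect and slowed speech, where nothing said or suspected points to a wish to die. Under section 11 the worker must assess self-harm risk and start the Plan. Under Appendix 3 the worker may email, decide that this is not a severe crisis, and leave. The deciding term has no definition, so two staff members could act differently on the same facts, each following the manual. What is at stake is participant safety at a home visit. Sample size, error rate and the primary analysis are not involved.

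**Working it through.** The plan gives no figure here to reproduce. The check is a side-by-side reading.

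1. **Trigger for the Plan.** Section 11: severe depression, or expressed thoughts of death or suicide. Appendices 3 and 4: severe crisis in the staff member's judgement.

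2. **Could severe crisis simply mean severe depression?** Each appendix uses the two terms in consecutive sentences with different actions. If they meant the same, the email sentence would have no separate purpose. Sections 8.1 and 10.1 mention crisis situations and crisis intervention without defining either.

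3. **Can severe depression be detected without talk of dying?** Of the six signs in section 11, one is a statement of not wanting to live. The other 6 − 1 = 5 (grooming, state of the house, weight loss, affect, speech) are not.

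4. **Order of actions.** In section 11 the email comes after the visit and reports what was done. In the appendices it is the first action.

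5. **Assessment visits.** Table 5 schedules the PHQ-9 at baseline and at follow-up (months 6 and 12). Section 11 says that it contains a question on being better off dead or hurting oneself. In Appendix 4 any non-zero answer to question 9 leads to the Columbia scale. Section 10.2.1 also has the Outcome Assessor ask about suicidal ideation at 6 and 12 months. A severely depressed participant at these visits is therefore already asked directly.

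6. **Treatment sessions.** Six initial and three booster sessions are planned, 6 + 3 = 9 per participant. No PHQ-9 is scheduled at them, and the instruction on depression for the interventionists is Appendix 3, item 8. This shows where the gap lies; it does not measure harm.

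7. **The general call rule.** Section 10.3.1 covers both kinds of visit: "For in-home assessments and treatment visits, staff will be instructed to call the PI if they encounter a situation that may warrant medical attention". Its events of concern extend to other symptomatic conditions that staff observe. Severe depression may fall within this but is not named, and the only psychiatric example is suicidal ideation.

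8. **Section 11's own gap.** Where a wish to die is neither indicated nor suspected, the opening sentence requires a risk assessment, but the only explicit step that follows is the statement of concern. The closing paragraphs assume that staff have spoken with the clinician, yet set no call during the visit.

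9. **Precedence.** Section 7.1 has all team members read the manual, and section 11 has all staff trained to use the Plan when indicated. Staff therefore meet both rules, and neither provision ranks them. The low alerting threshold in section 7.9 concerns suicidal ideation.

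**The case against.** The strongest reply is that the texts can be read together. The appendices are general instructions. They do not forbid starting the Plan, they point back to it, and section 11 asks for an email too. Staff are trained on the Plan, and section 10.3.1 gives them a route to the PI at every home visit. Suicidal patients are excluded, and severe depression is a baseline ineligibility disposition in section 5.5. Much of this stands: it limits the practical gap mostly to treatment sessions, and to cases missed at baseline or arising later. It does not settle when the Plan is indicated, which is the question the two texts answer differently.

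A reader might infer more than the documents support:

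- *That following the appendices skips the Columbia scale, the call and the no-leave rule.* Section 11 prescribes these only when a wish to die is indicated or suspected. What is lost in the case at issue is the general duty to assess risk, the scripted statement and the start of the Plan.
- *That no other safeguard reaches this participant, because none names severe depression as its trigger.* That is a point about wording. Question 9 is put to every participant at assessments regardless of voiced ideation, and the section 10.3.1 call may apply.
- *That the email might not reach the psychiatrist.* The appendix recipients are removed names, so nothing can be concluded either way.

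**Conclusion.** The inconsistency is in the current text and should be removed, as a minor patient-safety harmonisation. Two rules in one manual prescribe different actions for suspected severe depression, one of them depends on an undefined threshold, and neither is given precedence. The appendices do not cancel section 11, and it would be wrong to say that severely depressed participants are left unprotected.

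The number affected cannot be derived. Section 6.2 puts clinically significant depressive symptoms at 25% of persons with diabetes, but that is not the rate of severe depression without a wish to die among those randomised. The conclusion assumes that staff may act on their appendix as written. The benefit exists only if home visits continue, which the documents do not say; they state only that recruitment ended early with 156 randomised.

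**What to change.** In Appendix 3, item 8, and Appendix 4, item 8, replace the severe-crisis condition with section 11's trigger: where severe depression is suspected, judged by the signs listed in section 11, start the Plan during the visit, call the PI before leaving, and email afterwards. Keep the existing instructions for suicidal ideation.

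In section 11, after the statement of concern, add a direct question about thoughts of death or self-harm and the call to the PI, with the Columbia scale if such thoughts are indicated or suspected. At assessments PHQ-9 question 9 can serve as this question, so nothing is asked twice. If visits are still running, tell visiting staff of the change.

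The cost is wording in two appendix items, a short addition to section 11, and a few more in-visit questions and calls to the PI. How many cannot be derived from the documents.
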